4.2.6 Definition of End of study

The study will end when the last patient will have either withdrawn (including follow-up period of 30 days) from the study or completed the study (24 weeks + follow up period of 30 days) from the start of treatment (EPO or EPO+DFX DT or EPO+DFX FCT), whichever occurs earlier.

4.2.7 Study Day definition

For safety variables and analyses that requires using the safety set, study day will be defined as the number of days since the date of first dose of study drug (after randomization or enrollment). For a particular date on or after first dose, it will be calculated as:

Study day = Assessment date – Date of first dose of study drug + 1.

Therefore, the date of the first dose of study drug will be **Day 1** by definition.

The day before this day will be defined to be Day -1, i.e., there will be no Day 0. Study days before first dose of study drug will be calculated as

Study day = Assessment date – Date of first dose of study drug.

4.2.8 Treatment period

Having completed the screening period, patients are enrolled and randomized to receive either DFX DT or DFX FCT plus EPO or EPO alone. Study treatment is defined as DFX DT 10 mg/kg/day p.o. or DFX FCT 7 mg/kg/day p.o. plus EPO 40,000 units/week s.c. once weekly or EPO 40,000 units/week once weekly s.c.. EPO dose changes are allowed in both arms according to the EPO guidelines (see Appendix 3 of the CSP). For details on study design and dose adjustments, see Section 4.1 of the protocol. The study treatment duration is 24 weeks. After randomization, patient visits will occur weekly during the first month because key safety assessments need to be performed weekly in the first month of treatment and then every 4 weeks thereafter until week 24. In case of a dose increase of EPO after 4 weeks of treatment, an additional visit needs to be performed after 2 weeks of dose increase. For details of assessments, see Table 7-1 and Table 7-2 of the CSP.

4.2.9 Baseline

In general, for safety variables, the baseline value is defined to be the last available value prior to or on the day of first dose of study drug. For efficacy variables, the baseline value is defined to be the last available value prior to or on the day of randomization.

This definition does not apply for the following exceptions, where a specific definition was used:

- Serum creatinine: baseline value is defined as the mean of visit 1 and 2.
- Serum ferritin: baseline value is defined as the mean of visit 1 and 2.

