6.3.1.2 Elevations in serum creatinine

Serum creatinine should be monitored during the study as stated in the visit evaluation schedule [Table 7-1](#).

During the treatment period, patients who develop an increase in serum creatinine $\geq 33\%$ above their baseline value (average of visit 1 and 2) resulting in a serum creatinine above the upper limit of normal (ULN), on two consecutive occasions, the dose of the study drug will be reduced to 5 mg/kg/day for DFX DT and 3.5 mg/kg/day for DFX FCT until serum creatinine returns to below the age adjusted ULN.

It is recommended to check fluid balance and ensure adequate hydration of the patient.

In case of a single increase in serum creatinine, the assessment will be repeated in 2 weeks.

If after a dose reduction, a progressive increase in serum creatinine beyond the age adjusted ULN is observed, a treatment interruption is recommended.

After an interruption, if serum creatinine falls below the age appropriate ULN range on two consecutive visits, it is recommended to resume DFX DT therapy at 5 mg/kg/day or DFX FCT therapy at 3.5 mg/kg/day, and after 1 month, if the serum creatinine increase does not recur, study medication can be re-escalated to the standard dose of DFX DT at 10 mg/kg/day or DFX FCT at 7 mg/kg/day.

Caution should especially be used in patients with CrCl between 40 and less than 60 mL/min, particularly in cases where there are additional risk factors that may impair renal function such as concomitant medications, dehydration, or severe infections.

DFX therapy must be discontinued in case serum creatinine >2 times the age-appropriate upper limit or if CrCl <40 mL/min.

[figure not shown]
If after dose reduction, a progressive increase in serum creatinine is observed, Novartis must be contacted.

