7.2.2.4.2 Clinical chemistry

Clinical chemistry samples will be collected at Screening Visits 1 and 2, at Randomization Visit 3 and weekly for the first four weeks of study drug administration at Visits 4, 5, 6, at Visit 7 and then at 4 week intervals, thereafter, as described in the [Laboratory Manual]. Parameters to be measured will include: albumin, alkaline phosphatase, ALT/SGPT, AST/SGOT, bicarbonate, calcium, chloride, creatinine, glucose, inorganic phosphorus, potassium, sodium, C-reactive protein, creatine kinase, direct bilirubin, indirect bilirubin, total bilirubin, total cholesterol, LDL, HDL, total protein, triglycerides, blood urea nitrogen (BUN) or urea, uric acid, gamma-glutamyl transpeptidase (GGT).

In accordance with the DFX label, serum creatinine, creatinine clearance, alkaline phosphatase, ALT/SGPT, AST/SGOT, direct bilirubin, indirect bilirubin, total bilirubin must be assessed in duplicate before the initiation of therapy to establish a reliable pre-treatment baseline.

In addition, serum creatinine, alkaline phosphatase, ALT/SGPT, AST/SGOT, direct bilirubin, indirect bilirubin, total bilirubin will be measured weekly for the first four weeks of study drug administration at Visits 4, 5, 6.

Creatinine clearance will be estimated using the Cockcroft-Gault equation. This estimate will be provided each time serum creatinine is collected.

Serum ferritin test will also be performed at Screening Visits 1 and 2 to assess the eligibility of the patient. The baseline serum ferritin value is defined as the average of the two measurements obtained during the screening period. Serum ferritin testing will also be performed monthly starting at Randomization Visit 3.

Endogenous EPO will be assessed at Screening Visit 1 to assess the eligibility of the patient.

Fe/TIBC (TSAT), B12 and Folate will be performed at Screening Visit 1 to assess eligibility to EPO treatment. Fe/TIBC (TSAT) will be additionally assessed at therapy initiation at Visit 3 and then monthly.

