2.10.3 Laboratory data

All laboratory values will be converted into SI units and the severity grade calculated using the low/normal/high classifications based on laboratory normal ranges and for selected parameters by notable and extended ranges as available in the deferasirox program standards.

Note that, Hemoglobin (g/dL) and Serum Ferritin (ng/mL) are the only exceptions which will be reported in US-units (if appropriate).

Table 2-4 Criteria for clinically notable and extended laboratory ranges

Parameter	Criteria
Absolute neutrophils	<1.5×10 ⁹ /L (extended range <0.5×10 ⁹ /L)
Platelets	<100×10 ⁹ /L (extended range <50×10 ⁹ /L)
ALT/AST	>5×ULN and >2×baseline value (extended range >10×ULN and >2×baseline value)
Serum creatinine	> 33% increase from baseline and >ULN at two consecutive measurements at least 7 days apart
Creatinine clearance	<60 mL/min at two consecutive measurements at least 7 days apart (extended range <40 mL/min)
Urinary total protein/creatinine ratio	>113.1 mg/mmol at two consecutive measurements at least 7 days apart

The frequency of laboratory abnormalities will be displayed by parameter and treatment group. Laboratory data will be summarized by presenting summary statistics of raw values at baseline and changes from baseline (absolute) to worst post-baseline value and by treatment group.

Laboratory data will be summarized by presenting **shift tables** showing baseline versus most extreme post-baseline result by notable range.

Box plots of absolute value will be provided for selected parameters.

Listings of all laboratory data with values flagged corresponding to normal/notable/extended ranges will be provided. The listing of all laboratory values will be provided by planned and actual dose along with the columns for treatment arm to which the patient was randomized and the treatment arm where the patient belongs at the time of the assessment will be provided.

Hematology:

Box plots on absolute value for Hb, neutrophil and platelets corresponding to each visit will be provided.

Absolute change from baseline to worst post-baseline value (the lowest for hematology parameters) will be provided for Hb, neutrophil and platelets.

Absolute change from baseline to last available value at the time of EOT will be provided for Hb, neutrophil and platelets.

Listings will be provided for Hb, platelets and neutrophils as well.

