Creatinine clearance - Baseline categories: < 40 mL/min, $40 - < 60$ mL/min, $60 - < 90$ mL/min, $90 - < 160$ mL/min, ≥ 160 mL/min and Missing;

Creatinine clearance - Post-baseline categories: Two consecutive values measured at least 7 days apart < 60 mL/min, One value < 60 mL/min, Two consecutive values measured at least 7 days apart $60 - <90$ mL/min, One value $60 - <90$ mL/min, two consecutive values measured at least 7 days apart $90 - < 160$ mL/min, One value $90 - <160$ mL/min, ≥ 160 mL/min and Missing.

Creatinine clearance - Classification II:

Creatinine clearance - Baseline categories: < 40 mL/min, 40 - < 60 mL/min, 60 - < 90 mL/min, 90 - < 160 mL/min, ≥ 160 mL/min and Missing;

Creatinine clearance - Post-baseline categories: Two consecutive values measured at least 7 days apart < 40 mL/min, One value < 40 mL/min, Two consecutive values measured at least 7 days apart 40 - <60 mL/min, One value 40 - <60 mL/min, ≥ 40 mL/min and Missing

Calculation for CrCl:

In the formula below, CrCl denotes creatinine clearance, SCr denotes serum creatinine in μmol/L; age in years will be calculated from date of birth and date of the relevant blood sample. Weight and height will be the last available measurements at the time of the relevant blood sample.

Cockcroft-Gault formula (≥18 years of age),

CrCl (mL/min) =

Male patients: $(140 - \text{age}) \times \text{weight} / (815 \times 0.001 \times \text{SCr})$

Female patients: $(140 - \text{age}) \times \text{weight} \times 0.85 / (815 \times 0.001 \times \text{SCr})$

Note 1: The recalculated creatinine clearance in derived Lab data and standard UNITCONV data:

- Parameter names (PARNAM1C) as 'CRCLSCG' for Cockcroft-Gault formula.
- Preferred (PREUNT1C) and Converted (CNVUNT1C) unit 'mL/min' for Cockcroft Gault formulae.
- Zero Precision (CNVPCS1N) for converted values.

Note 2: For Height and Weight, last available values at the time of assessments should be used. Current age should be derived at the time of assessments.

Listings will also be provided for serum ferritin, ALT, AST, total bilirubin, serum creatinine, creatinine clearance and urinary protein/creatinine ratio.

A listing of all laboratory values will be flagged as appropriate and will be provided along with planned and actual dose (EPO and EPO + DFX). Assessment day relative to first dose of study drug will be included.

All other blood chemistry parameters apart from the ones mentioned above will only be listed.

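### Baseline creatinine clearance is taken from a different blood sample than baseline creatinine, so the two renal changes from baseline can disagree for the same patient

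*SAP*

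**What the plan says.** SAP 4.2.9 states the general rule for safety data: "the baseline value is defined to be the last available value prior to or on the day of first dose of study drug". It lists two exceptions: "Serum creatinine: baseline value is defined as the mean of visit 1 and 2" and "Serum ferritin: baseline value is defined as the mean of visit 1 and 2". CrCl is not listed, so the general rule applies to it.

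The creatinine exception agrees with protocol 6.3.1.2, where a rise is judged "above their baseline value (average of visit 1 and 2"), and with the eligibility rule (protocol 5.2, criterion 9), which also uses the mean of the two screening values.

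Protocol 7.2.2.4.2 names CrCl among the tests that "must be assessed in duplicate before the initiation of therapy to establish a reliable pre-treatment baseline".

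SAP 2.10.3 calculates CrCl by Cockcroft-Gault from the creatinine, age and weight belonging to the relevant blood sample ("SCr denotes serum creatinine in" µmol/L). The same section reports both creatinine and CrCl as change from baseline to the worst value and to end of treatment, and in shift tables with baseline categories. Protocol 10.5.11.3 adds relative CrCl change by category.

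**The concern.** Age and weight hardly move over 24 weeks, so a patient's CrCl is in effect the reciprocal of creatinine on a different scale. The two changes from baseline ought to tell one story. Under SAP 4.2.9 they need not, because the Visit 3 sample sets the CrCl baseline and plays no part in the creatinine baseline.

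A chance high or low creatinine at Visit 3 therefore shifts every later CrCl change for that patient and leaves the creatinine changes untouched. It can also place the patient in a CrCl baseline row that the duplicate screening values do not support.

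This falls on results that the trial wants. The Amendment 3 rationale in the protocol gives additional renal safety data as a reason for the common CrCl limit, and inclusion criterion 10 admits patients at 40 to <60 mL/min at the investigator's discretion. That range is one of the baseline rows in the CrCl shift tables. With 60 patients randomized 1:1, each arm has about 30, so a few misplaced patients change a row visibly.

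**Working it through.** The plan states no figure on this point, so there is none to reproduce. The check establishes which samples are used, then what follows from that.

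**1. Samples used**

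- First dose is at Visit 3 (protocol 4.1). Chemistry is drawn at Visit 3 (protocol 7.2.2.4.2), and CrCl is calculated at every visit (Table 7-1, footnote 6).
- Baseline creatinine = (V1 + V2)/2. Baseline CrCl = CrCl at V3. If V3 is missing, CrCl falls back to V2, still a single reading.

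**2. Formula (SAP 2.10.3, men)**

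CrCl = (140 − age) × weight / (0.815 × SCr)

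**3. Attenuation.** Constructed case: man, 74 years, 75 kg; creatinine 90, 90 and 108 µmol/L at Visits 1 to 3, later 120.

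- Numerator: 66 × 75 = 4950.
- SCr 90: 4950/73.35 = 67.5 mL/min. SCr 108: 4950/88.02 = 56.2. SCr 120: 4950/97.8 = 50.6.
- Creatinine change: 120/90 = 1.333, or +33%.
- CrCl change as the SAP is written: 50.6/56.2 = 0.90, or −10%.
- CrCl change on the Visit 1–2 baseline: 50.6/67.5 = 0.75, or −25%.
- CrCl baseline category: 40 to <60 as written; 60 to <90 on the Visit 1–2 baseline.

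**4. Reversal.** Constructed case: man, 72 years, 70 kg; creatinine 80, 80, 100, then 90 µmol/L at end of treatment.

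- Numerator: 68 × 70 = 4760. CrCl is 73.0 at SCr 80, 58.4 at 100 and 64.9 at 90.
- Creatinine: +10/80 = +12.5% (worse).
- CrCl as written: 58.4 to 64.9 = +11.1% (better).
- CrCl on the Visit 1–2 baseline: 73.0 to 64.9 = −11.1% (worse), in line with creatinine.

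**5. Frequency of opposite directions at one post-baseline visit.** Take log creatinine with independent errors of equal variance (1 unit) and no true change.

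- Creatinine change: variance 1 + ½ = 1.5. Change relative to V3: variance 1 + 1 = 2. Covariance 1.
- Correlation = 1/√(1.5 × 2) = 1/√3.
- P(opposite directions) = arccos(1/√3)/π = 0.304, whatever the CV.

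The documents give no within-patient CV, so 5%, 7.5% and 10% are assumed. Simulation with 1,000,000 patients gives:

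| True creatinine rise | CV 5% | CV 7.5% | CV 10% |
|---|---|---|---|
| none | 30.4% | 30.4% | 30.4% |
| 10% | 10.1% | 18.6% | 23.1% |
| 20% | 0.6% | 5.1% | 11.1% |
| 33% | 0.0% | 0.4% | 2.7% |

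With no true change, opposite changes of at least 10% in both measures occur in 0.01%, 0.38% and 1.6% of patients. For the change to the worst of nine post-baseline values (Visits 4–7, 9–12 and end of treatment), the directions disagree in about 13% (CV 5% and 10%).

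**6. With a common baseline.** If baseline CrCl is calculated from the mean Visit 1–2 creatinine, opposite directions fall to 0% at constant age and weight. If it is the mean of the two CrCl values, 0.8% (CV 5%) to 1.6% (CV 10%) remain with no true change.

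**The case against.** The last pre-dose value is an accepted baseline, closest to the start of treatment. It is defined identically in both arms, so it creates no systematic difference between them, and the tables are descriptive. The protocol asks for CrCl in duplicate but does not prescribe a mean. Where it wants a mean it says so, for creatinine and ferritin, and those are exactly the two that the SAP averages. Derivations and baseline categories are partly assigned to Modules 7 and 8, which are not available, and listings of both measures would expose any disagreement.

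Much of this stands. It does not answer the narrower point: once creatinine has been given a two-visit mean, a quantity computed from creatinine cannot keep another baseline without the two becoming inconsistent. Unseen modules cannot be presumed to override SAP 4.2.9, and a listing does not correct a summary table.

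A reader might infer more than the documents support:

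- **Large contradictory renal signals.** The first case above shows attenuation: both measures worsen. True reversals are possible but mostly small, and they become rare as the real creatinine rise grows.
- **Distorted notable flags.** The CrCl limits in Table 2-4 (<60, extended <40 mL/min) do not involve baseline. The creatinine flag needs more than a 33% rise and a value above ULN at two consecutive measurements at least 7 days apart, so a single sample cannot trigger it.
- **The same fault for liver tests.** The ALT/AST criterion requires >5×ULN as well as >2× baseline. Entry requires ≤2×ULN, so any value above 5×ULN exceeds 2.5 times a baseline within that limit. The baseline condition can matter only if the baseline is at least 2.5×ULN. In the SAP, alkaline phosphatase is only listed, and bilirubin appears in neither Table 2-4 nor the shift tables. Averaging these tests would be a preference, not a correction.

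**Conclusion.** The point holds for CrCl alone. As written, SAP 4.2.9 compares creatinine and CrCl with different baseline samples. This can weaken or occasionally reverse a patient's CrCl change relative to creatinine and can move the patient to another baseline row of the CrCl shift table.

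It is a fault of consistency and precision in the renal safety tables. It does not touch the primary endpoint and is unlikely to hide a large renal effect. The precision loss is moderate: under equal, independent variation, a two-reading baseline lowers the variance of a change from 2 to 1.5 units, a cut of 25%, or about 13% in SD.

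The mismatch itself rests on the text. The 30.4% rests on independent, equal within-patient variation and no true change. The remaining percentages also depend on the assumed CVs, and both patients are constructed.

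**What to change.** In SAP 4.2.9, add CrCl to the exceptions: baseline CrCl is calculated by Cockcroft-Gault from baseline creatinine, the mean of Visits 1 and 2. State which age and weight enter. Weight is scheduled at Screening Visit 1 and again at Visit 3, so the last weight available at Visit 2 is normally the Screening Visit 1 value.

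Use this baseline in the CrCl change-from-baseline, relative-change and shift tables, and align the derivations in Modules 7 and 8. Deriving CrCl from the mean creatinine is preferable to averaging two CrCl values, because it removes the disagreement completely at constant age and weight.

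The cost is one SAP line and the matching programming; the samples are already scheduled. The small downside is that the Visit 3 value, closest to first dose, no longer sets the CrCl baseline, as is already so for creatinine.

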As the EPO guidelines only provide guidance for EPO use (EPO dosing, dose adjustments and dose discontinuation) and do not specify any criteria for the evaluation of erythroid response in MDS patients, in this study, the primary objective erythroid response will be assessed according to IWG criteria (Hb increase ≥ 1.5 g/dL) at 12 weeks of treatment. At any time, if Hb ≥ 12 g/dL, EPO will be stopped until the end of study. Patients treated with the combination therapy will stop EPO if Hb ≥ 12 g/dL and continue on DFX.

At 24 weeks, patients initially assigned to the combination therapy who showed Hb increase ≥ 1 g/dL at week 12 will be assessed for full hematological response according to IWG criteria (Erythroid response: Hb increase from baseline ≥ 1.5 g/dL; Neutrophil response: increase from baseline of $\geq 100\%$ and $> 0.5 \times 10^9/L$; Platelet response: increase from baseline of $\geq 30 \times 10^9/L$).

Patients initially treated with EPO alone and switched to the combination therapy with EPO and DFX after 12 weeks will be assessed for erythroid response at study end after 24 weeks of study treatment.

Figure 4-1 Study Design

Pre-treatment phase (Screening)

At Screening Visit (Visit 1) the investigator or his/her designee will assign a unique number to patients being considered for the study.

Prior to performing any study-related procedures or assessments, the patient must provide written consent to participation in this study. A screening period (up to 28 days) will be used to assess patient eligibility. Two Screening Visits will be required because key safety parameters need to be performed twice before the first dose administration ([Table 7-1](#)).

This study will use an Interactive Web Response (IWR) technology for randomization. Once the patient provides a signed informed consent form and eligibility is confirmed (all inclusion/exclusion criteria have been verified) the investigator and/or his designee can register the patient using the IWR.

Treatment phase

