7.1.1 Screening

Prior to commencement of the screening examination, the patient must have given full informed consent and have completed the study Informed Consent form. Once this has been signed and dated by the patient then the investigator can take the patient through the study inclusion and exclusion criteria to make sure that the patient is fully eligible to participate.

The full list of assessments to be performed during the screening period (week -4 to week -1) is detailed in [Table 7-1](#) and [Table 7-2](#). Two Screening Visits that are at least 14 days apart are needed to perform key safety parameters prior to first dose administration as specified in the label.

Re-screening is permissible on a case by case basis. Please contact Novartis for guidance and see [Section 7.1.1.2](#) to get information on how to process screen failures.

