4.2 Definitions

4.2.1 Study drug and study treatment

Study treatments refers to EPO and EPO+DFX DT or EPO+DFX FCT.

Study drugs are DFX and EPO.

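### SAP 4.2.9 sets no baseline at the switch, so EPO-arm patients who start DFX after 12 weeks have their lab changes measured from before EPO

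*SAP*

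**What the plan says.** The general rule in SAP 4.2.9 for the safety tests is "the baseline value is defined to be the last available value prior to or on the day of first dose of study drug". It then exempts two tests. One exemption reads "Serum creatinine: baseline value is defined as the mean of visit 1 and 2"; serum ferritin is treated the same way. There is no exemption for patients who change regimen.

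SAP 4.2.1 says "Study drugs are DFX and EPO". An EPO-arm patient's first dose is therefore the first EPO dose, which Protocol 4.1 places at Visit 3. Protocol 4.1 and SAP 2.2 move EPO-arm patients to the combination after 12 weeks if Hb has risen by less than 1 g/dL and is below 12 g/dL.

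SAP 2.10.3 uses the baseline for changes to the worst and to the end-of-treatment value, for the rows of the shift tables, and for two notable criteria: creatinine more than 33% up, and ALT/AST more than twice baseline, each combined with a ULN condition. The section groups results by treatment. It does not say which group switchers belong to, or whether their weeks 1-12 values can count as the worst value.

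Elsewhere the SAP does split at the switch: section 2.7.2 counts switchers' DFX exposure from week 13, and section 2.10.2 reports their adverse events for weeks 13-24 only.

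Protocol 7.2.2.4.2, referring to the DFX label, requires that renal and liver tests "must be assessed in duplicate before the initiation of therapy to establish a reliable pre-treatment baseline". The dose rule in Protocol 6.3.1.2 measures a creatinine rise "above their baseline value (average of visit 1 and 2").

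**The concern.** In the combination arm, the start of study treatment and the start of DFX coincide, so one baseline serves both. In switchers the two are 12 weeks apart. A laboratory change measured after the switch then contains whatever happened on EPO alone as well as whatever happened on DFX, and the summaries cannot separate them.

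Renal safety is a declared interest of this trial. The Amendment 3 rationale wants additional renal data on the combination, inclusion criterion 10 can admit patients with creatinine clearance from 40 to below 60 mL/min, and Protocol 1.2.1.2 reports mild creatinine rises in about 36% of DFX-treated patients. Modest relative changes of that kind are the ones most easily blurred by a baseline that predates the drug. Switchers are the only DFX-exposed patients besides those randomised to the combination.

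**Working it through.** **Inputs.** "A screening period (up to 28 days) will be used to assess patient eligibility" (Protocol 4.1). "Two Screening Visits that are at least 14 days apart are needed to perform key safety parameters prior to first dose administration" (Protocol 7.1.1). "Clinical chemistry samples will be collected at Screening Visits 1 and 2, at Randomization Visit 3 and weekly for the first four weeks" (Protocol 7.2.2.4.2). Visit 3 is Day 1, and Visit 10 is nominally Day 84 with a window of Day 77 to 91 (SAP Table 4-1). There is no Day 0, so the gap from Day -d to Day D is D + d - 1 days, and from Day 1 it is D - 1.

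**Serum creatinine (mean of Visits 1 and 2).** The earliest closely spaced pair is Days -28 and -14; the latest is Days -15 and -1.

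- Switch on Day 84, earliest pair: (111 + 97)/2 = 104 days = 14.9 weeks.
- Switch on Day 84, latest pair: (98 + 84)/2 = 91 days = 13.0 weeks.
- Switch on Day 77, latest pair: (91 + 77)/2 = 84 days = 12.0 weeks.
- Switch on Day 91, earliest pair: (118 + 104)/2 = 111 days = 15.9 weeks.

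So the gap is 13.0 to 14.9 weeks nominally and 12.0 to 15.9 across the window. SAP Table 4-7 (S06) treats only a delay of more than one week as a deviation; a switch on Day 98 would take the upper figure to 16.9 weeks.

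**ALT, AST, bilirubin, creatinine clearance, urine protein/creatinine ratio (general rule, normally Visit 3).** Nominal: 84 - 1 = 83 days = 11.9 weeks. Across the window: 76 to 90 days = 10.9 to 12.9 weeks.

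**Combination arm, creatinine.** The same pairs lie (28 + 14)/2 = 21 days = 3.0 weeks, or (15 + 1)/2 = 8 days = 1.1 weeks, before Day 1. The switchers' excess is the 83 days on EPO alone.

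**Effect on the baseline-relative component.** Suppose creatinine has drifted by a fraction x on EPO alone. The further rise on DFX that reaches 33% above baseline is 1.33/(1 + x) - 1. For ALT/AST, twice baseline becomes 2/(1 + x) times the value at the switch. The documents give no drift, so x is an assumption, shown over a range.

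| Assumed drift on EPO alone | Further creatinine rise to reach 33% | ALT/AST multiple of switch value |
|---|---|---|
| -20% | 66.3% | 2.50 |
| -10% | 47.8% | 2.22 |
| 0 | 33.0% | 2.00 |
| +10% | 20.9% | 1.82 |
| +20% | 10.8% | 1.67 |

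**What does not depend on the baseline (SAP 2.10.3).** The creatinine criterion also needs values above ULN, confirmed on a second consecutive sample. ALT/AST also needs more than 5 times ULN. The limits for creatinine clearance (60 and 40 mL/min) and urine protein ratio (113.1 mg/mmol) are absolute. Most post-baseline shift categories are absolute or ULN-based.

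**Samples available.** Protocol Table 7-1 schedules chemistry and urine protein ratio at Visits 9 and 10 (nominal Days 56 and 84). By their windows these visits are at least 77 - 63 = 14 days apart, the same minimum as the screening pair. Their mean is centred (84 - 56)/2 = 14 days, or 2 weeks, before a nominal switch.

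**The case against.** The laboratory analyses are descriptive, in a pilot of about 60 patients. SAP 2.10.1 lists the true treatment at each assessment, and SAP 1.1 leaves derivations to Module 8, which is not among the documents. The Amendment 3 rationale sees no evidence that EPO alone affects renal safety. These points limit the weight of the concern but do not remove it. Listings do not re-base a summary table, and section 4.2.9 reads as a complete definition. The EPO statement concerns the intravenous route, whereas EPO here is subcutaneous, and drift over 12 weeks need not be caused by EPO.

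Some stronger readings are tempting but are not supported:

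- A reader might infer that every renal and liver baseline is 13 to 17 weeks old. Only creatinine and ferritin use the screening mean; the other tests are about 12 weeks old, and about 17 weeks for the creatinine mean requires a delayed switch.
- A reader might infer that the creatinine flag stands for anything from an 11% to a 66% rise on DFX. That range rests on assumed drifts of ±20% and ignores the ULN and repeat conditions.
- A reader might infer that the combination arm's creatinine baseline is taken immediately before DFX. It is the same screening mean, 1.1 to 3.0 weeks before Day 1.
- A reader might infer that Protocol 6.3.1.2 and 7.2.2.4.2 contradict each other. The two screening visits are the required duplicate; both sections are simply silent on the switch.

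One objection shapes the remedy. Replacing the baseline outright would alter the ferritin secondary endpoint (SAP 2.9.2.4) and detach the creatinine flag from the Protocol 6.3.1.2 rule and deviation S12. That stands, so the new baseline should be an addition.

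**Conclusion.** The gap is real and worth closing, but it is confined to the safety summaries of switchers; the primary analysis is untouched. In those patients, roughly 12 weeks on EPO alone are mixed with the DFX weeks in change-from-baseline summaries, shift-table baseline rows, and the 33% and twice-baseline components.

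It would go too far to say that drift on EPO will be reported as DFX toxicity or will conceal it. That can happen in baseline-relative summaries, but it depends on how switchers are grouped, which SAP 2.10.3 leaves open, and on a drift that the documents do not quantify.

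The number of switchers is also not stated. The 40% reference response rate in SAP 2.11 does not supply it, because response means a rise of at least 1.5 g/dL at any time in 12 weeks, whereas the switch depends on a rise below 1 g/dL after 12 weeks. The conclusion assumes that Module 8 contains no separate baseline for switchers.

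**What to change.** In SAP 4.2.9 and 2.10.3, add a supplementary DFX-phase baseline for switchers, using only values before the first DFX dose:

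- Serum creatinine: the mean of Visits 9 and 10.
- ALT, AST, bilirubin, creatinine clearance and urine protein/creatinine ratio: the last pre-DFX value.

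Use it to summarise switchers' weeks 13-24 changes, shifts and baseline-relative flags as a separate group. State that weeks 1-12 values do not count as their worst value on DFX. Keep the existing baseline as a second display, and leave the ferritin and Hb secondary endpoints on their defined baselines.

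No change to the dose rule in Protocol 6.3.1.2 is proposed. The sponsor should only make clear what baseline means in that section for a patient who starts DFX at the switch.

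The cost is SAP wording, one derived variable and an extra set of tables. No new samples are needed.
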